(v) *Patient randomization.* Randomization will be performed as we have previously published. To keep birth-weight distribution comparable in the two groups, we will use five 250-gram-birth weight strata for randomization. To ensure equal enrollment in the two groups, infants will be randomly assigned within each stratum, according to a permuted block design to receive inhaled nitric oxide (INOmax®, INO Therapeutics) or

oxygen placebo. This strategy provides a balanced group assignment with every 4 enrollments.

(vi) *Patient enrollment at study entry procedures.* We will enroll patients and enter them into the study as we have previously published. Briefly, potential subjects will be identified, prenatally if possible, and the parents approached for informed consent. With consent obtained, and the infant born, admitted, and verified to meet inclusion criteria, a sealed envelope containing the randomized treatment assignment, appropriate identifying labels, etc., will be pulled and opened by the respiratory therapist. Documentation of the treatment assignment and patient data will be recorded by the respiratory therapist in the study book (kept in the respiratory therapy room), and an INOvent® brought to the bedside. The INOvent will be set to deliver either iNO or oxygen according to the treatment randomization and then covered to conceal the treatment group from the caregivers and investigators.

(vii) *Treatment.* iNO or placebo (oxygen) will be given 5 ppm while ventilated or on continuous positive airway pressure (CPAP) and 10 ppm while on nasal cannula oxygen. In infants receiving iNO by nasal cannula, iNO concentrations are set to 10 ppm, because previous studies have shown that delivery 10 ppm by nasal cannula results in nasopharyngeal concentrations of about 5 ppm^9. These dosages will continue until the infant no longer needs supplemental oxygen or reaches 33 weeks post conceptional age. All infants will have iNO delivery devices (INOvents) at the bedside to deliver either iNO or O2, and will be shrouded to hide from caregivers the nature of the gas being delivered. Only respiratory therapy and data safety monitor to know of gas assignments.

(viii) *Data Collection.* Clinical data (fluids, medications, diagnoses, ventilator settings) will be collected daily by our research professional.

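### Blocks of 4, printed in the protocol, let the respiratory therapists who open the envelopes and keep the assignment book deduce about one in three assignments in advance

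*Combined protocol and SAP*

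**What the plan says.** All of this is in the combined protocol and SAP, Research Plan, Specific Aim #1.

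- **(v) Patient randomization.** For birth weight, "we will use five 250-gram-birth weight strata for randomization". The aim is 1:1 ("To ensure equal enrollment in the two groups"), and "infants will be randomly assigned within each stratum, according to a permuted block design". The section then adds: "This strategy provides a balanced group assignment with every 4 enrollments".
- **(vi) Enrollment and study entry.** After consent, birth, admission and confirmation of eligibility, a sealed envelope "will be pulled and opened by the respiratory therapist". Then "Documentation of the treatment assignment and patient data will be recorded by the respiratory therapist in the study book", which stays in the respiratory therapy room. The device is covered so that caregivers and investigators do not see the group.
- **(vii) Treatment.** "Only respiratory therapy and data safety monitor to know of gas assignments".

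No varying block size, central allocation or limit on access to the book is described. Sections (v) and (vi) both refer to an earlier publication for the procedure, which is not available here.

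**The concern.** One group on a single unit holds three things together: the balancing interval, the record of every earlier assignment, and the unopened envelopes. With that information the end of each block can be worked out before the envelope is opened.

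Foreknowledge does harm when it can affect who is entered, or when. Section (iii) allows entry up to 72 hours of age, with consent before birth or in the first three days, so the order of entry within a stratum is not wholly fixed. Section (iv) includes a physician's judgement of viability. Section (vi) says that eligibility is verified but not by whom. If the next assignment were known to anyone with a say at those points, the arms could differ at baseline in ways that adjustment would not reliably repair. A failure of concealment cannot be corrected after enrolment.

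**Working it through.** The plan gives no figure for predictability, so there is none to reproduce.

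**Inputs.** Block length 4, inferred from (v). Allocation 1:1 and five strata, from (v). Planned enrolment 268, from (ix) Sample size. Assumption: enrolment spread evenly over strata, 268/5 = 53.6, taken as 54.

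**Complete blocks of 4.** There are 6 orderings of two A and two B.

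- AABB and BBAA: after two assignments, the last 2 are certain.
- The other four: only the last 1 is certain.
- Certain per block: (2×2 + 4×1)/6 = 1.333. Share: 1.333/4 = **33.3%**. By position: 0, 0, 1/3, 1.
- Best-guess success: (1/2 + 2/3 + 2/3 + 1)/4 = **70.8%**, against 50% with no foreknowledge.

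**At 54 per stratum.** This is 13 complete blocks plus 2 infants.

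- Certain: 13×1.333/54 = 17.33/54 = **32.1%**.
- Best guess: (13×2.833 + 1/2 + 2/3)/54 = 38.0/54 = **70.4%**.

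Simulating 268 infants over five strata, with incomplete last blocks, gives 32.6% certain, about 87 infants (0.3256×268). An uneven spread over strata gives the same share.

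**Dependence on the inferred block length.** Blocks of 2 also balance after every 4, and would make 1/2 of assignments certain. On the stated balance alone, the fourth of every four is always forced, so the floor is 1/4.

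**Alternatives.** Simulated for an observer who has the full stratum history and knows which sizes are in use (equally likely), but not the size of any given block, at 54 per stratum:

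| Scheme | Certain | Best guess correct | Largest within-stratum imbalance |
|---|---|---|---|
| Blocks of 4 | 32% | 70% | 2 |
| Mixed 2/4/6, concealed | about 4% | about 70% | 3 |
| Mixed 4/6/8, concealed | about 2% | about 68% | 4 |

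Mixed 2/4/6 blocks cut certain foreknowledge about eight-fold (32/4) but leave guessing almost unchanged.

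**The case against.** The strongest reply is that the people who can deduce the next assignment are not shown to be the people who enrol. Only respiratory therapy and the data safety monitor know the gas. Nothing in the documents has either group approach parents, take consent or decide eligibility. The envelope is pulled only after consent and the eligibility check; the stratum follows from birth weight; the Oxygen Index limit is numeric; and viability is judged by a physician, who as a caregiver is meant to be blinded. Devices stand shrouded at the bedside in both arms. Blocks of 4 with sealed envelopes are also a recognised choice where balance in small strata is wanted.

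Most of this stands. A reader might infer that one in three allocations is in fact known to those who decide entry. The documents do not support that: 33.3% is what could be deduced from the complete stratum history, and bias would need a leak or therapist influence on entry or timing, neither of which is documented. A reader might also infer that outcome assessment is compromised. Section (xv) says that all examiners are unaware of assignment, and the block length does not change that.

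It is also fair that a constant block size is inferred and that the earlier publication may give more detail on how lists and envelopes are prepared. What remains is that eligibility is verified by an unnamed person, therapists are not excluded from that step, and the interval is printed in the protocol.

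**Conclusion.** The point holds as a weakness in allocation concealment that is cheap to close. It is not evidence of selection bias. Under blocks of 4, someone with a stratum's history can deduce 33.3% of assignments in complete blocks and about 32% at the planned size. That ability is confined to respiratory therapy and the data safety monitor unless information leaks.

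The conclusion rests on three assumptions: that the stated balance means blocks of 4 within each stratum, that enrolment is near 268, and, for the mixed-block figures, that the possible sizes are equally likely and known to the observer. A reader might infer that varying the block size makes allocation essentially unpredictable. It does not: it removes most certainty, but best-guess success stays near 70%. The sample size and the planned analysis do not change.

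**What to change.** 1. Generate each stratum's list with randomly varying block sizes, for example 2, 4 and 6 or 4, 6 and 8.
2. Remove the balancing interval from the protocol, and keep the sizes in a document that unit staff, including respiratory therapy, do not see.
3. Name an existing team member, blinded to earlier assignments, to record eligibility with date and time before the therapist pulls the envelope. As guessing stays near 70% under mixed blocks, this step carries much of the protection and should not be dropped in favour of the first two alone.

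**Cost.** A new list and one extra entry per infant. Within-stratum imbalance can reach 3 instead of 2 with sizes up to 6, or 4 with sizes up to 8. If all five strata stopped at their worst point in the same direction, the overall difference would be 5×3 = 15 or 5×4 = 20 infants, against 5×2 = 10 now. Enrolment target, treatment and analysis stay as planned.

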- 3) Specific design of the study to assess neurodevelopmental outcome. Our previous study had been designed to assess the effect of iNO treatment on the incidence of chronic lung disease and death; we assessed these infants' neurodevelopmental outcomes because of our unanticipated finding of decreased brain bleeding and softening. This study has as its primary outcome the incidence of abnormal neurodevelopmental outcome.
- 4) Laboratory-based Specific Aim to assess the mechanisms of the iNO-induced neuroprotection.

**Specific Aim #1. Assess the role of iNO therapy on neurodevelopmental outcome in all oxygen-dependent premature infants having birth weights < 1500g.**

(i) *Rationale.* We have previously found that brief (1 week) treatment of ventilated preterm infants reduces abnormal neurodevelopmental outcome. Because brain development continues throughout gestation, we hypothesize that iNO therapy will be protective to the preterm brain if given from birth until the risk for abnormal neurodevelopmental outcome is similar to that of term infants.

(ii) *Study design.* We have designed a randomized, placebo controlled, double blind study of iNO therapy during Intensive Care Nursery stay, followed by blinded neurodevelopmental assessment at 18 months corrected age, a commonly used developmental endpoint.

(iii) *Patients.* All premature infants cared for in the Intensive Care Nursery at the University of Chicago Medical Center, who are less than 72 hours old, weighing less than 1500 grams at birth, and requiring any respiratory support, will be eligible for the study. Enrolled infants are anticipated to have the same demographics as we have previously reported: 52% male, 70% African-American, 45% single parent household. Potential subjects will be identified and informed consent sought, if possible, prior to birth, otherwise, within the first 3 days after birth.

(iv) *Exclusion criteria.* Those infants with severe congenital anomalies, including major congenital heart disease, or major kidney, lung or brain malformations will be excluded, as will be those infants with a genetic syndrome. Infants judged by the physician to not be viable will be excluded from the study, as will extremely sick infants requiring very high ventilatory pressures (Oxygen Index  $\geq 20$ ). This latter group is excluded because of a previous study by Van Meurs which showed that infants in this category are made worse by inhaled nitric oxide.

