(ix) *Sample size.* In our previous study of infants with RDS, iNO treatment cut the risk of abnormal neurodevelopmental outcome by half. The baseline incidence of abnormal neurodevelopmental outcome is 40% in this age group by published NICHD data. Therefore to see a decrease of abnormal neurodevelopmental outcome to 20% (half of baseline incidence) with 80% power, 82 babies are needed in each arm of the study, for a total of 164 babies. We have previously published an overall mortality rate for intubated infants < 2000g in our nursery of 23%. Because we are including non-intubated infants, we

estimate a mortality rate of about 18%. Therefore, to ensure sufficient infants surviving to follow up, we anticipate needing to enroll approximately 215 babies over 18 months. With a historic 80% follow-up rate, we will need a total of 268 infants. Every year we admit approximately 175-200 infants with birth weights < 1500g. We therefore anticipate enrollment taking as long as 18 months. Our non-consent rate historically is < 10%.

(x) *Standards of neonatal intensive care.* Because we have shown no effect of ventilatory strategy on neurodevelopmental outcome, there will be no external control of ventilatory modality. Because this is a single-site study, variability in practice exists only between our eight member group of neonatologists, with constant care provided by nurse practitioners, residents, and nursing staff.

(xi) *Safety monitoring.* As per our clinical routine, methemoglobin is regularly monitored with arterial blood gases. Although we and others have shown that iNO therapy is safely used in preterm infants, interim safety analyses will be performed when 50% of patients enrolled. Deaths will be compared, as will the incidence of severe intraventricular hemorrhage, and tests of significance made with Chi-square. The study will be stopped if the incidence of either index in the iNO groups is significantly higher than in placebo groups.

(xii) *Primary Outcome.* As we have published, we will measure abnormal neurodevelopmental outcome at 18 months corrected age. Three disability levels will be assessed: disability (cerebral palsy, blind in both eyes, or deaf in both ears); delay (score on Mental or Psychomotor Developmental Index of the Bayley Scales of Infant Development < 70 without a disability) or normal (without disability or delay).

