## Appendices

### A. Project schedule/Timeline of events

Time	Project Stage	Activity
Year 1 month 1	Begin patient enrollment	randomize to NO or placebo
	Begin assessment of NO delivery and metabolism during hospitalization	measurement of arterial and venous nitrite and nitrosylated hemoglobin
year 1 month 3	anticipate 1st discharges to home - assess complications of prematurity potentially affecting neurodevelopmental outcome	Routine head ultrasounds Routine head MRI at discharge Classification of chronic lung disease
year 1 month 9	Interim safety analysis	Comparison of death rates and rates of Grade IV IVH between groups
Year 2 month 7	End patient enrollment	
	Begin assessment of 18 month neurodevelopmental outcome	Bayley scales Neurologic exam Assessment of CP status Assessment of Blindness Assessment of hearing
Year 2 month 7		
Year 3 month 12	End 18 month neurodevelopmental outcome assessment	

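### The enrolment target of 268 does not follow from the stated 18% mortality and 80% follow-up, which give 250, and 18 months is not an upper limit on accrual

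*Combined protocol and SAP*

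**What the plan says.** All the figures are in Specific Aim #1, (ix) Sample size, unless another place is named.

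- **Core size.** The plan states "The baseline incidence of abnormal neurodevelopmental outcome is 40% in this age group" and aims to detect a fall to 20% with 80% power. This takes 82 infants per arm, 164 in total.
- **Mortality.** The nursery's published rate in intubated infants under 2000 g was 23%. Because non-intubated infants are now included, the authors "estimate a mortality rate of about 18%. Therefore, to ensure sufficient infants surviving to follow up, we anticipate needing to enroll approximately 215 babies". The period attached to that number is 18 months.
- **Follow-up.** "With a historic 80% follow-up rate, we will need a total of 268 infants".
- **Accrual.** "Every year we admit approximately 175-200 infants with birth weights < 1500g". The paragraph continues: "We therefore anticipate enrollment taking as long as 18 months. Our non-consent rate historically is < 10"%.
- **Eligibility.** Sections (iii) and (iv) require respiratory support. "Those infants with severe congenital anomalies, including major congenital heart disease, or major kidney, lung or brain malformations will be excluded", as are infants with a genetic syndrome, infants judged not viable, and infants with an Oxygen Index of 20 or more. No eligible fraction is given.
- **Schedule.** Appendix A starts enrolment in year 1 month 1, puts the interim safety analysis at year 1 month 9, and enters "End patient enrollment" at year 2 month 7.

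**The concern.** The text presents 215 as the consequence of 18% mortality, but the division does not give 215. The next step is consistent with 215, so the discrepancy passes into the final total. The 18-month period is attached first to 215 and then, unchanged, to 268, which is 25% larger (268/215 = 1.25).

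The trial is run on both figures. The total decides when half the infants are enrolled, and so when the interim safety analysis falls: at 134 infants under 268, or 125 under 250. The accrual period underlies the Appendix A dates. As written, a reader cannot reproduce the total or rely on the end date.

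**Working it through.** **1. Core size (reproduces).** Inputs: 40% against 20%, 80% power, 1:1 allocation. Alpha is not stated. Two-sided 0.05 is assumed because it returns the plan's own figure; one-sided 0.05 would give 64 per arm. With pooled variance under the null:

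n = [1.96 × √(2 × 0.30 × 0.70) + 0.8416 × √(0.40 × 0.60 + 0.20 × 0.80)]² / 0.20² = 81.2, so 82 per arm and 164 in total.

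**2. Inflation for losses (does not reproduce).**

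| Step | Stated | From the stated inputs |
|---|---|---|
| Mortality 18% | about 215 | 164/0.82 = 200 |
| Follow-up 80% | 268 | 200/0.80 = 250 |

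The second step is consistent with the number it starts from: 215/0.80 = 268.75. The fault is in the first step, where 215 implies mortality of 1 − 164/215 = 23.7%. Multiplying by 1.18 instead of dividing by 0.82 gives 194, so that common slip does not explain it. The 23% rate quoted just before gives 164/0.77 = 213 and 213/0.80 = 266, close to both stated figures. A rate that was not updated is therefore plausible, but the plan does not say so.

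**3. What each total delivers** (same test, 40% against 20%).

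| Enrolled | Mortality | Follow-up | Evaluable | Power |
|---|---|---|---|---|
| 268 | 18% | 80% | 268 × 0.82 × 0.80 = 176 | 83% |
| 250 | 18% | 80% | 250 × 0.82 × 0.80 = 164 | 80% |
| 268 | 23% | 80% | 268 × 0.77 × 0.80 = 165 | 81% |
| 250 | 23% | 80% | 250 × 0.77 × 0.80 = 154 | 78% |

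A total of 268 keeps 164 evaluable up to mortality of 1 − 164/(268 × 0.80) = 23.5%.

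**4. Accrual.** Months = N / (admissions per year × consent) × 12, with every admission treated as eligible.

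| N | Refusals | 200 a year | 175 a year |
|---|---|---|---|
| 215 | 10% | 14.3 | 16.4 |
| 250 | 0% | 15.0 | 17.1 |
| 250 | 10% | 16.7 | 19.0 |
| 268 | 0% | 16.1 | 18.4 |
| 268 | 10% | 17.9 | 20.4 |

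At 175 a year, 18 months brings 175 × 1.5 = 262.5 admissions, fewer than 268. At 200 a year it brings 300, so 268 needs 268/300 = 89% of admissions to be eligible with no refusals, and 268/270 = 99% at 10% refusals. Before any exclusion, 18 months does hold for 215.

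**5. If enrolment stopped at 18 months** with 175 admissions a year and 10% refusals: 175 × 1.5 × 0.90 = 236 enrolled, 236 × 0.82 × 0.80 = 155 evaluable, about 78% power.

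**The case against.** The strongest reply is that nothing is harmed. The slip over-enrols by 18 infants and raises power from 80% to 83%. The 23% rate in the same paragraph nearly explains it, perhaps as a deliberate margin. Cutting the target to 250 would remove that margin against a mortality figure that is itself an estimate. This stands as an argument about size and about the choice of repair. It does not make 215 follow from 18%, and the plan claims no margin.

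On accrual, the 18 months is a forecast. The stated refusal rate is below 10%, so 20.4 months combines a bound on refusals with the lowest admissions. With no refusals the worst overrun is 0.4 months, and Appendix A may span 18 to 19 months depending on how month 7 is counted. The Significance section also describes infants needing some respiratory support as the great majority of premature infants. Nothing says that enrolment closes at 18 months whatever the count, so the 78% is a scenario and not a prediction. These points keep the overrun modest on the stated figures. They do not make 18 months an upper limit, since the low end of the plan's own admission range exceeds it before any refusal or exclusion.

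Finally, 250 depends on the 80% follow-up used in this section. Specific Aim #1, (xiv) gives drop-out below 15%; at 85% follow-up the need would be 200/0.85 = 236. That moves further from 268, not closer.

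**Conclusion.** Both parts hold. On the stated inputs the enrolment target is 250; the plan's 268 is 18 infants (7%) higher because 215 does not follow from 18% mortality. The error is conservative: 268 gives about 176 evaluable infants and 83% power, assuming two-sided 0.05, 18% mortality and 80% follow-up.

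Eighteen months is not an upper limit for 268. Over 175 to 200 admissions a year, with every admission eligible, it takes 16.1 to 18.4 months with no refusals and 17.9 to 20.4 months at 10% refusals. Correcting to 250 does not fully cure this (up to 19.0 months). Exclusions lengthen accrual by an amount the documents do not give.

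The point should be fixed because the headline total cannot be reproduced and the end date cannot be relied on. It is not a threat to power if 268 infants are enrolled.

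**What to change.** In Specific Aim #1, (ix), do one of the following:

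- Keep 268 and say what it delivers: about 83% power at 18% mortality and 80% follow-up or, equivalently, 80% power with mortality up to about 23.5%. This is the cheapest sound option, because it preserves the margin and leaves the design alone.
- State the inputs actually used to obtain 215.
- Restate the target as 250 (164/0.82/0.80), accepting about 78% power if mortality turns out to be 23%.

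State alpha and sidedness in the same sentence. Tie the accrual period to one enrolment total, and give it as a range computed from admissions × consent × an eligible fraction that the plan states and labels as an estimate.

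The cost is one reworded paragraph. The interim date (year 1 month 9) and the end-of-enrolment date (year 2 month 7) in Appendix A need to change only if a longer accrual period is stated.

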In our previous study, we found that some infants tolerated our standard weaning protocol from iNO poorly, requiring much slower weaning and therefore a longer time on very low concentration (1-2 ppm) of NO. One mechanism underlying this minor complication is decreases in native NO production by blood vessels of the lung during prolonged periods of iNO delivery. Therefore, it is conceivable that extremely preterm infants, who will, by design, receive iNO for up 8 or 9 weeks, exhibit intolerance to weaning off iNO. Accordingly, we will wean patients by 1 ppm every 12-24 hrs, the protocol which served us well in the previous study in this setting.

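### Deaths and severe IVH are compared between arms only once, at 50% enrolment; add one harm-only look at 75%, with the significance level and sidedness stated at each look.

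*Combined protocol and SAP*

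**What the plan says.** The stopping rule is in Specific Aim #1, (xi) Safety monitoring. The timing is that "interim safety analyses will be performed when 50% of patients enrolled". Deaths and severe IVH are compared by chi-square, and the consequence is fixed: "The study will be stopped if the incidence of either index in the iNO groups is significantly higher than in placebo groups". The plan gives no significance level, sidedness, size of harm to be detected, minimum follow-up or analysis set for this test.

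Appendix A lists one interim safety analysis, at year 1 month 9, described as "Comparison of death rates and rates of Grade IV IVH between groups". Enrolment ends at year 2 month 7, and no later safety comparison appears. The IVH index is severe IVH in (xi) but Grade IV in Appendix A.

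On size, (ix) Sample size says: "With a historic 80% follow-up rate, we will need a total of 268 infants". It also estimates mortality at about 18%. On exposure, (xvii) says that extremely preterm infants "will, by design, receive iNO for up 8 or 9 weeks". Section (vii) Treatment names a data safety monitor who knows the gas assignments, but no review schedule or decision rule is given for that role.

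**The concern.** The rule can act only on what is known at mid-enrolment. A difference just short of significance at month 9 has no scheduled re-examination while about 134 more infants are randomised. Treatment of up to 8 or 9 weeks is longer than the one week in the sponsor's previous trial and the 3 weeks in one of the cited trials. The exclusion criteria also cite a trial in which very sick infants did worse on iNO. Evidence of harm that builds up during the second half therefore matters, and the plan sets no point at which to look for it.

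**Working it through.** **Inputs.** From (ix): 268 infants in total and planning mortality of 18%, applied here to placebo. From (v): balanced allocation. From (xi): chi-square, stopping only if iNO is worse. Assumed: two-sided 5% (z > 1.96), and iNO mortality of 28% or 36% (doubled), since the plan names no target harm.

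**Reproducing the plan's own figure.** The plan sets out "to see a decrease of abnormal neurodevelopmental outcome to 20% (half of baseline incidence) with 80% power" and concludes that "82 babies are needed in each arm of the study, for a total of 164 babies". With pooled variance and no continuity correction:

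n = [1.96·√(2·0.30·0.70) + 0.84·√(0.40·0.60 + 0.20·0.80)]² / 0.20² = (1.270 + 0.532)² / 0.04 ≈ 81.2, so 82 per arm.

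This matches exactly. One-sided 5% would give 64, so two-sided 5% is the natural level to assume for the safety test too.

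**The 50% look.** 268/2 = 134 infants, 67 per arm.

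Power = Φ{[Δ − 1.96·√(2·p̄(1−p̄)/n)] / √[(p₁(1−p₁) + p₂(1−p₂))/n]}

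- 18% vs 28%: Δ = 0.10, p̄ = 0.23. (0.10 − 0.1425)/0.0722 = −0.589, giving 27.8%. Exact binomial enumeration gives 27.9%.
- 18% vs 36%: Δ = 0.18, p̄ = 0.27. (0.18 − 0.1503)/0.0751 = 0.395, giving 65.4%. Exact: 65.8%.
- No true difference (18% in both arms), exact: 2.5% false stops on deaths.

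In counts, with 12 placebo deaths (18% of 67), 21 iNO deaths give z = 1.80 and do not stop the trial; 22 give z = 1.99 and do.

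**Sensitivity for 18% vs 28%.** One-sided 5%: 39%. Half of the 215 infants also mentioned in (ix), about 54 per arm: 23%. All 268 infants (134 per arm): 49%. Reaching 80% would need 277 per arm.

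**Adding a look at 75%.** 0.75 × 268 = 201, about 100 to 101 per arm. Chance of stopping on deaths at either look, by exact enumeration over both looks:

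| Rule | No difference | 18% vs 28% | 18% vs 36% |
|---|---|---|---|
| 50% only, z > 1.96 | 2.5% | 28% | 66% |
| 50% and 75%, z > 1.96 at both | 3.9% | 44% | 85% |
| 50% at z > 1.96, 75% at z > 2.2 | 3.1% | 38% | 80% |

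To separate added information from a looser threshold, the same enumeration was run for a single 50% look at z > 1.80. It gives 3.8% false stops, 34% and 72%. So about 6 of the 16 points gained for 18% vs 28% could be had by loosening the existing look; the rest comes from the extra infants.

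**Both indices.** If the IVH test had the same false-stop chance and were independent of deaths, the combined chance would be 1 − (1 − 0.025)² = 4.9% now, 1 − (1 − 0.039)² = 7.6% with z > 1.96 at both looks, and 1 − (1 − 0.031)² = 6.1% with z > 2.2 at the second.

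**Incomplete follow-up at the look.** Assuming even accrual, 268/18 = 14.9 infants a month, or about 3.43 a week. Those enrolled in the last 8 to 9 weeks number 3.43 × 8 = 27 to 3.43 × 9 = 31 of 134. This is an upper bound on infants still on gas.

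**The case against.** **The 28% figure is not the plan's, and the look is not solely to blame.** This stands. The plan names no harm to be detected, even full enrolment gives about 49% for a 10-point excess, and the result depends on an unstated level. A reader might infer that any serious excess of deaths would probably go undetected. The documents do not support that: doubled mortality would be caught about two times in three at the existing look, and severe IVH is a second route that these figures omit.

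**More looks gain detection partly by stopping falsely more often.** This also stands, and it limits the remedy. Looks at 25%, 50% and 75%, all at z > 1.96, give 46% and 86%, but with 5.5% false stops on deaths. Held to about 2.5%, three looks give only 33% for 18% vs 28% by the last look, and 21% by the 50% look, below the present plan. A 25% look is therefore not worth asking for.

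**The look is said to count infants still on gas.** That is an inference from a trigger based on enrolment. No analysis set is stated, and many infants stop gas earlier because they no longer need oxygen. Restricting the comparison to infants who have finished gas or died would be worse. It keeps every death but drops survivors still on gas, and time on gas may itself depend on treatment.

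**Oversight exists after month 9.** There is a data safety monitor, clinical data are collected daily, and methemoglobin is checked routinely. A reader might infer that nobody watches the second half of the trial; the text does not say so. What is missing is a second scheduled comparison between arms.

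**Conclusion.** The concern holds in limited form. The plan schedules one comparison of deaths and severe IVH, at half enrolment, and none while about 134 further infants are enrolled and treated. At an assumed two-sided 5% level with 18% placebo mortality, that look would stop the trial on deaths with a chance of about 28% for an illustrative 10-point excess and 66% for a doubling. One further look at 75% would raise these to about 44% and 85%, or 38% and 80% with the stricter second threshold, for a modest rise in false stops on deaths. These figures rest on 268 infants enrolled, deaths fully observed at each look, and deaths alone. This is an inexpensive improvement to safety monitoring; it does not show that the existing look is invalid.

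**What to change.** In Specific Aim #1, (xi), and in Appendix A:

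1. Keep the 50% look and add one look at 75% enrolment (about 201 infants), on the same two indices and in the harm direction only, as the rule already is.
2. State the significance level and sidedness at each look, for example z > 1.96 at both, or z > 1.96 and then z > 2.2. Give the resulting false-stop chance for the two indices together.
3. State that all randomised infants are in the comparison and how incomplete follow-up is handled, for example with a time-to-death comparison.
4. Reconcile the IVH index, which is severe IVH in (xi) and Grade IV in Appendix A.

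The cost is one more tabulation for the data safety monitor from data already collected daily, and a false-stop chance on deaths of 3.9% or 3.1% in place of 2.5%, higher with both indices counted. Because the rule can stop only for harm, the added look does not inflate the false-positive rate of the final efficacy test.
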